Envarsus XR in African American Renal Transplant Recipients

NCT Number: NCT02956005

Date: 07/25/2016

Study Protocol

Title: Envarsus XR in African American Renal Transplant Recipients

Introduction

Tacrolimus is overwhelmingly used as an immunosuppressant in kidney transplantation, both early posttransplantation and as part of long-term maintenance regimens. While highly effective in preventing acute transplant rejection, tacrolimus has several limitations, including a narrow therapeutic window (necessitating drug monitoring and individual dose titration), interindividual variation in absorption, and low bioavailability of the currently widely used immediate-release tacrolimus (IR-Tac) twice-daily capsule formulation (Prograf; Astellas Pharma US, Inc).¹ In addition, both the IR-Tac formulation and another extended-release once-daily tacrolimus formulation (Advagraf/Astagraf XL; Astellas Pharma US, Inc) are associated with similar peak concentrations²; unwanted tacrolimus-associated neurologic adverse events (AEs) have been noted to happen or be most pronounced at peak serum tacrolimus blood concentrations. Additionally, the twice-daily formulation adds further pill burden to a patient population already encumbered with taking many long-term medications. Multiple daily drug dosing is associated with increased risk for nonadherence; this may result in acute rejection and, in severe cases, transplant failure.

The medication LCP-Tacro (LCPT; Envarsus XR; Veloxis Pharmaceuticals) is an extended-release tablet formulation of tacrolimus with once-daily dosing that has been developed using a proprietary MeltDose drug delivery technology (Veloxis Pharmaceuticals), distinguishing LCPT from other once-daily extended-release tacrolimus

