products (eg, Astagraf XL). The MeltDose technology decreases a drug's particle size to the smallest possible units as single molecules. Drug particle size critically affects drug dissolution and absorption; if particle size is smaller, the surface area of the drug increases and the drug will be dissolved more quickly, resulting in better absorption. Results of the MeltDose technology are increased absorption and bioavailability associated with LCPT tablets compared with other extended-release and IR tacrolimus formulations currently available. Phase 1 and phase 2 trials confirmed that LCPT enables broader absorption throughout the gastrointestinal tract and sustains consistent tacrolimus concentrations⁴. In addition, LCPT showed a lack of diurnal variability common with other formulations.

Phase 2 trials of de novo and stable kidney and liver recipients showed a steadier and more consistent concentration-time profile over 24 hours, with reduced peak and peak-to-trough fluctuations for LCPT compared to IR-Tac, increased bioavailability of ~30%, and comparable efficacy and safety profiles. A robust correlation between the area under the curve at 24 hours and the minimum concentration was also shown, indicating that therapeutic drug monitoring of minimum concentration as a measure of tacrolimus exposure can be applied to LCPT. A phase 3 conversion trial showed that LCPT had noninferior efficacy and comparable safety profile to IR-Tac, with lower doses (~20% lower than IR-Tac overall and 30% lower in white patients) of LCPT⁵.

Hypothesis

African American renal transplant recipients that receive Envarsus will have less tubular injury and calcineurin inhibitor toxicity compared with patients that receive tacrolimus IR.

Study Type/Design

This is a case control study where a prospective cohort will be started de novo on Envarsus at the time of renal transplantation.

Endpoints

Primary endpoint is to determine the rate of calcineurin inhibitor toxicity as measured by surveillance kidney biopsies.

Secondary endpoint is to determine the rate of development of donor specific antibodies of the patients treated with Envarsus vs the patients treated with immediate release tacrolimus.

Patient Recruitment

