We will prospectively consent 100 African American patients that will be receiving kidney transplants at our center. This cohort will be matched with a retrospective cohort of African American renal transplant recipients who received renal transplant and were treated with immediate release tacrolimus.

Exclusion criteria will include patients that are not African American and patients that are younger than 18 years old.

Inclusion Criteria

1. African American race

2. Adult renal transplant recipients (≥ 18 y/o)
3. Previous adverse reaction or contraindication to the use of tacrolimus

Exclusion Criteria

1. Non African American race
2. Less than 18 y/o (pediatric patients)
3. Recipients of liver and small bowel transplants
4. Adverse reaction to tacrolimus

Statistical analysis:

Data will be analyzed using standard statistical methods using chi square test, students T-square test, kaplan-meyer curve. No statistical analysis has been performed to achieve adequate power as this an observational study.

Treatment Overview

Screening will be performed by the Principal Investigators during the kidney transplant evaluation clinics, during the wait list kidney transplant evaluation clinic and prior to a schedule kidney transplant surgery.

Dosage and Administration of Envarsus XR

Patients enrolled in the prospective arm of the study will be started on Envarsus XR at 0.17mg/kg. The dose will be targeted to achieve a tacrolimus level between 8-10 ng/mL.

The tacrolimus level will be modified depending on the results of the surveillance biopsy, BK and CMV viruses, and donor specific antibody studies.

Laboratory Testing and Study Schedule

Schematic diagram of data that will be obtained during study:

Data to be obtained at time 0 on the prospective and retrospective cohort

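### Inclusion criterion 3 demands a tacrolimus reaction or contraindication, contradicts exclusion criterion 4, and shuts out the ordinary recipients the study means to enrol

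*Combined protocol and SAP*

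**What the plan says.** The protocol states eligibility in three places.

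- Inclusion Criteria, item 3: "Previous adverse reaction or contraindication to the use of tacrolimus". Items 1 and 2 of that list are African American race and adult renal transplant recipient.
- Exclusion Criteria, item 4: "Adverse reaction to tacrolimus". Items 1 to 3 cover race, age, and liver or small bowel transplants.
- Patient Recruitment, the sentence above the lists: "Exclusion criteria will include patients that are not African American and patients that are younger than 18 years old". It does not mention tacrolimus history.

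The treatment is fixed elsewhere. Under Study Type/Design, "a prospective cohort will be started de novo on Envarsus at the time of renal transplantation". Under Dosage and Administration, "Patients enrolled in the prospective arm of the study will be started on Envarsus XR at 0.17mg/kg". The Introduction says that Envarsus XR "is an extended-release tablet formulation of tacrolimus with once-daily dosing". The matched retrospective controls were treated with immediate-release tacrolimus. Patient Recruitment plans for 100 African American kidney recipients at the center and does not mention intolerance of tacrolimus.

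**The concern.** Inclusion 1 and exclusion 1 are complements (race), and so are inclusion 2 and exclusion 2 (age). Inclusion 3 and exclusion 4 break that pattern: they describe the same kind of patient, once as someone to take and once as someone to refuse. Item 3 reads like an exclusion that landed in the wrong list.

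Eligibility is a rule that the site carries out. Followed literally, this one turns away the population under study and admits patients for whom the study drug is contraindicated. If the investigators sensibly ignore it, every ordinary recipient enrolled is a deviation from the written criteria.

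A second, smaller matter is timing. Item 3 refers to a previous reaction, but exclusion 4 has no time anchor, and the protocol does not say whether the numbered criteria apply to the retrospective cohort. Historical charts also hold events after transplant. If exclusion 4 were applied to whole charts, controls who reacted to immediate-release tacrolimus after transplant could be dropped, leaving controls selected for tolerance. The endpoint at stake is stated as follows: "Primary endpoint is to determine the rate of calcineurin inhibitor toxicity as measured by surveillance kidney biopsies".

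**Working it through.** There is no figure in the plan to reproduce, so the check is logical. Let A = adverse reaction to tacrolimus and C = contraindication to tacrolimus, for a patient who meets the race, age and organ criteria.

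Inputs:
- Inclusion item 3 requires (A or C).
- Exclusion item 4 removes A.
- Assumption: all inclusion items must be met together. The protocol does not say so, but this is the natural reading of a list whose first two items are race and adult recipient.

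Rule as written: eligible = (A or C) and not A, which reduces to C and not A.

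| Reaction (A) | Contraindication (C) | Meets inclusion 3 | Hit by exclusion 4 | As written | Item 3 deleted only: not A | Item 3 merged into exclusion 4: not (A or C) |
|---|---|---|---|---|---|---|
| no | no | no | no | **not eligible** | eligible | **eligible** |
| no | yes | yes | no | **eligible** | eligible | not eligible |
| yes | no | yes | yes | not eligible | not eligible | not eligible |
| yes | yes | yes | yes | not eligible | not eligible | not eligible |

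Eligible combinations: 1 of 4 as written, and it is the wrong one; 2 of 4 if item 3 is simply deleted, one of them still the contraindicated patient; 1 of 4 after merging, the intended patient.

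Other readings:
- *Contraindication means only a previous reaction.* Then C equals A, and (A or A) and not A is empty. Nobody is eligible.
- *Inclusion items are alternatives.* Ordinary recipients pass, but so do contraindicated patients without a reaction, because exclusion 4 names reactions only.
- *The Patient Recruitment sentence is the whole rule.* All 4 combinations pass. Its wording is not exhaustive, however, and it also leaves out exclusion 3, so it cannot be relied on to override the list.

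The text yields the intended patient only if the first two of these readings are combined, and the protocol states neither.

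Could a tacrolimus-intolerant population be deliberate? The rest of the protocol says no. The study drug is tacrolimus, the controls took tacrolimus, and Potential Pitfalls and Contingencies treats tacrolimus side effects as a possible reason to change regimen.

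On recording: the time-0 list under Laboratory Testing and Study Schedule has 11 items, and 0 of them capture tacrolimus history.

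**The case against.** The strongest reply is that the intent is obvious. The hypothesis, the de novo start and the recruitment paragraph all describe ordinary recipients, and "Screening will be performed by the Principal Investigators", who know whom they want. On this view the line is clerical, and no endpoint, dose or analysis depends on it. It is right about likely behaviour: dosing of contraindicated patients is a risk in the text and is not shown to have occurred. It does not rescue the rule, because nothing in the protocol overrides item 3 and correct enrolment would still breach the written criteria.

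Several narrower objections stand in part:

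- Screening takes place in the evaluation clinics and before surgery, so prospective eligibility is already settled before transplant. The timing gap therefore concerns only the retrospective cohort.
- The control-selection risk is conditional. No section says that exclusion 4 will be applied to post-transplant charts, and the documents do not equate a clinical reaction with toxicity seen on biopsy. If the two were linked, dropping controls who reacted would lower toxicity among controls and work against the Envarsus hypothesis.
- The 1-of-4 count is of logical combinations, not patients.
- The time-0 list also omits recipient race and age, so it is not an eligibility checklist. Its silence on tacrolimus history is no evidence of the contradiction.

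**Conclusion.** The concern holds. With the inclusion items jointly required, the written criteria admit only patients with a contraindication to tacrolimus and no reaction to it, or nobody if contraindication means a previous reaction. Either way they refuse the ordinary recipients whom the study is designed to treat. The conclusion rests on the joint-requirement assumption and on the absence of any overriding text. The protocol gives no prevalence for the patient types, so no number of affected patients can be given. The contradiction alone is enough to require correction before the criteria are used; the timing point for controls is secondary and conditional.

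**What to change.** 1. Remove item 3 from the Inclusion Criteria and merge it with exclusion 4 as one exclusion, for example: *any reaction to, or contraindication for, tacrolimus that was known before transplant*.
2. State that this exclusion applies to both cohorts and uses only information available before transplant. A reaction that first appears after transplant is then not an eligibility failure in either cohort, and controls who reacted to immediate-release tacrolimus stay in.
3. Make the exclusion sentence in Patient Recruitment agree with the list.
4. Preferably, add one yes/no item at time 0 for both cohorts recording a tacrolimus reaction or contraindication known before transplant, so that the criterion can be checked.

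The cost is one merged eligibility line with its scope stated, one corrected sentence and one extra chart item. The target of 100, the visits and the procedures are unaffected. Steps 1 and 2 are the essential ones; steps 3 and 4 tidy and document.

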1. BMI

2. Weight
3. Sex
4. Reason for chronic kidney disease
5. Induction agent
6. Crossmatch results
7. Type of donor
8. Donor age
9. Donor sex
10. Donor end creatinine
11. Donor's biopsy result if available

Data to be obtained at time 1 month, 3 month, 6 month and 12 month on the prospective and retrospective cohort

1. Creatinine level
2. Proteinuria
3. Tacrolimus level
4. Diabetes
5. Blood pressure
6. BK virus serum
7. CMV virus PCR
8. Donor specific antibody
9. Biopsy results (at 3 and 12 months surveillance and any other additional for cause biopsy that the patient may have had)

10. Infections
11. Hospital admissions
12. Blood transfusions (if any)

Patient Monitoring and Evaluation

Patients will have a kidney biopsy at time 0 (at the time of implantation and prior to reperfusion), 3 months and 12 months. If at any other time it is clinically necessary to perform another biopsy, it will be performed.

Potential Pitfalls and Contingencies

If a patient develops side effects that are attributed to tacrolimus, then the patient may have to be switched to another immunosuppression regimen.

References

1. Prograf [prescribing information]. Northbrook, IL: Astellas Pharma US, Inc; September 2013.

3. Bechstein WO. Neurotoxicity of calcineurin inhibitors: impact and clinical management. *Transpl Int.* 2000;13(5):313-26.

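### The non-randomised comparison with retrospective controls names no matching variables and no adjusted analysis, and gives the baseline data collected in both cohorts no role

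*Combined protocol and SAP*

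**What the plan says.** The Hypothesis section is comparative: patients on Envarsus are expected to have "less tubular injury and calcineurin inhibitor toxicity compared with patients that receive tacrolimus IR". The secondary endpoint, donor specific antibodies, is also stated as a comparison of the two drugs.

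The Study Type/Design section reads "This is a case control study where a prospective cohort will be started de novo on Envarsus at the time of renal transplantation". The comparator appears under Patient Recruitment: "This cohort will be matched with a retrospective cohort of African American renal transplant recipients" treated with immediate-release tacrolimus. That section gives 100 as the number of prospective patients. It gives no number of controls, matching variables, ratio, matching method or calendar window.

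The analysis plan is one sentence: "Data will be analyzed using standard statistical methods using chi square test, students T-square test, kaplan-meyer curve". The sentence after it says that no power calculation was done because the study is observational.

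Under Laboratory Testing and Study Schedule there is a list headed "Data to be obtained at time 0 on the prospective and retrospective cohort". Its eleven items include BMI, sex, induction agent, crossmatch, donor type, donor age and "Donor end creatinine", and it ends with the donor's "biopsy result if available". No sentence uses any of these items for matching, adjustment or a check of balance.

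**The concern.** The groups are formed by drug and by period, not by randomisation, so they may differ in anything that changed at the centre or that influenced who was transplanted and how. Matching can deal with part of this. How much cannot be judged while the variables are unnamed, and an unspecified match can also be settled after the retrospective outcomes are known. African American race and receipt of a kidney transplant are eligibility conditions common to both cohorts; they are not matching variables that balance risk within them.

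Any imbalance that remains passes straight into a chi-square test, a t-test or a Kaplan-Meier curve. It can produce an apparent benefit of Envarsus or conceal a real one. The primary endpoint is read from graft biopsies, and donor age, donor type and donor creatinine are plausible influences on graft histology. The documents do not call these items prognostic; that is a clinical judgement. The data needed to correct for measured imbalance are nevertheless already being collected.

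**Working it through.** **Reading check.** The documents contain no regression, stratification, propensity score, weighting, matched-pair analysis or balance table. They state no significance level, event rate or effect size, so there is no figure of the plan's own to reproduce. Everything below is an illustration on assumed inputs.

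**Assumed inputs.** 100 per cohort (the 100 prospective patients are stated; the number of controls is not); two-sided 5% test; no drug effect; one binary factor with toxicity risk *lo* = 20% without it and *hi* = 40% (or 50%) with it. The factor's prevalence is 45% v 55%, 40% v 60% or 35% v 65% (Envarsus v control), taken as the imbalance remaining after matching.

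**Formulas.**
- Cohort risk: p = prev × hi + (1 − prev) × lo.
- Null SE: s0 = √[2p̄(1 − p̄)/100], with p̄ the mean of the two risks.
- Actual SE: s1 = √{[pE(1 − pE) + pC(1 − pC)]/100}.
- False-positive rate: Φ[(d − 1.96 s0)/s1] + Φ[(−d − 1.96 s0)/s1], with d = |pE − pC|.

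**Example, 20 points, risks 20% and 40%.** pE = 0.40 × 0.40 + 0.60 × 0.20 = 0.28; pC = 0.60 × 0.40 + 0.40 × 0.20 = 0.32; d = 0.04; s0 = √(2 × 0.30 × 0.70/100) = 0.0648; s1 = √[(0.2016 + 0.2176)/100] = 0.0647. The first term is Φ(−1.34) = 0.089 and the second is Φ(−2.58) = 0.005, in total 9.4%.

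| Residual imbalance | Risks with hi = 40% | Spurious difference | Uncorrected | Continuity-corrected | Risks with hi = 50% | Spurious difference | Uncorrected | Continuity-corrected |
|---|---|---|---|---|---|---|---|---|
| 10 points | 0.29 v 0.31 | 2 points | 6.1% | 4.4% | 0.335 v 0.365 | 3 points | 7.3% | 5.2% |
| 20 points | 0.28 v 0.32 | 4 points | 9.4% | 7.1% | 0.32 v 0.38 | 6 points | 14.4% | 11.1% |
| 30 points | 0.27 v 0.33 | 6 points | 15.2% | 11.9% | 0.305 v 0.395 | 9 points | 26.5% | 21.7% |

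The continuity-corrected rates come from exact binomial enumeration. That test rejects 3.4–3.5% of the time when the cohorts are balanced.

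**Adjusted analysis.** Studies of 200 patients were simulated, 20,000 per scenario, and analysed by logistic regression on cohort, the factor and four unrelated covariates. The risk difference was standardised over the sample, with a delta-method SE. Risks of 10%/30%, 20%/40% and 20%/50% give about 40, 60 and 70 events; imbalance ran from 0 to 30 points. The type I error was 5.2–5.9% and the bias below 0.1 point. The 95% CI half-width was within 0.7 point of the raw one (for example 12.6 v 12.6 points). Smaller repeat simulations agreed within simulation error.

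**Masking.** Suppose Envarsus halves the risk, and its cohort has 60% with the 40%-risk factor against 40% in the controls. The raw risks are 0.5 × 0.32 = 0.16 and 0.28, a difference of 12 points. With equal prevalence (50%) they are 0.15 and 0.30, a difference of 15 points. Power is 54% raw and 73% adjusted. With a 10 point imbalance (0.155 v 0.29) it is 64% raw and 75% adjusted.

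**The case against.** The best reply is that confounder control is planned: the protocol promises matching, and the same items are collected in both cohorts, most naturally for that purpose. On this view the defect is a missing specification, and the larger figures above need a 20–30 point imbalance to survive matching in a factor that at least doubles risk. At 10 points the chi-square is close to nominal, and below it with continuity correction. The plan also sets no significance level, and the primary endpoint is worded as determining a rate.

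Much of this stands as a limit on the size. The documents give no ground for expecting any particular imbalance, and the illustration does not model the matching itself. It does not remove the point. No sentence ties the time-0 list to the matching, so nobody can say which factors will be balanced. The hypothesis and the secondary endpoint are comparative. The observational label is offered only as a reason for having no power calculation; for confounding it argues the other way.

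The simulation also favours adjustment: there is one measured confounder, the null model is correctly specified and every biopsy is observed. Its near-zero bias shows that the method works at this sample size, not that this study would be free of bias. Donor type and induction agent may have several levels or overlap poorly between the cohorts. Choosing model adjustment over fully specified matching with a balance table is partly preference, since either could address measured imbalance.

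**Conclusion.** The concern holds and should be fixed. On the text it is certain: the matching is unspecified, no analysis adjusts for baseline differences, and the time-0 data have no stated use. The size is conditional. With 100 per cohort and one factor that doubles the risk, the harm is small at 10 points of residual imbalance (6.1%), material at 20 (9.4%) and large at 30 (15.2%). It is greater for a stronger factor, and a true halving of risk can lose about 19 points of power (73% − 54%). These figures show the direction and possible size under assumptions; they are not estimates for this study. The comparison can still be run, but as written a difference could not credibly be attributed to Envarsus.

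**What to change.** 1. **Main analysis of the primary endpoint.** Use an adjusted risk difference with 95% CI, standardised from a logistic regression of toxicity on cohort and about five pre-named covariates: for example donor type, donor age, donor end creatinine, induction agent and recipient age. Group multi-level factors so that the model stays near five covariate parameters. Keep the raw chi-square as descriptive.
2. **Matching.** State the variables (from the same baseline items), the ratio, the method and the number of controls, and present a balance table. Use a conditional or pair-clustered analysis only if matching is individual.
3. **Data list.** Add recipient age, which must be known to apply the 18-year criterion, and transplant date.
4. **Calendar time.** Draw controls from a stated recent window. Do not match on transplant date, because prospective and retrospective cohorts differ in period by design. Report era confounding as a limitation that adjustment for measured variables cannot remove.
5. **Baseline histology.** Leave the donor biopsy out of the main model, because it is collected only where available. The Patient Monitoring and Evaluation section also describes a kidney biopsy at time 0; state whether that applies to the retrospective cohort, and how baseline histology will be reported.
6. **Design label.** Describe the study as a prospective cohort with matched retrospective controls, since the groups are formed by drug and not by outcome.

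**Cost.** No new patients or visits: revised wording, slightly more modelling and two added data items. The 40–70 events expected at assumed rates of 20–35% in 200 patients support only about five covariates. The adjusted test runs slightly above nominal (5.2–5.9%), and differences in unmeasured factors remain.

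### Target level and result-driven level changes are specified only for the Envarsus arm, so formulation may be confounded with exposure management

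*Combined protocol and SAP*

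**What the plan says.** The Hypothesis section compares the two formulations: less tubular damage and less calcineurin inhibitor toxicity is expected with Envarsus than with immediate-release tacrolimus. Under Endpoints, the primary endpoint is stated as follows: "Primary endpoint is to determine the rate of calcineurin inhibitor toxicity as measured by surveillance kidney biopsies". The secondary endpoint compares the rate of donor specific antibodies between the two treatments.

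Exposure rules appear only under Dosage and Administration of Envarsus XR:

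- The section opens with the arm it covers: "Patients enrolled in the prospective arm of the study will be started on Envarsus XR at 0.17mg/kg".
- It sets a target: "The dose will be targeted to achieve a tacrolimus level between 8-10 ng/mL".
- It then provides for changes: "The tacrolimus level will be modified depending on the results of the surveillance biopsy, BK and CMV viruses, and donor specific antibody studies".

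Patient Recruitment plans 100 prospective patients and a matched retrospective cohort, defined as African American recipients "who received renal transplant and were treated with immediate release tacrolimus". It gives no matching variables, control number, era, target level or adjustment practice.

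Laboratory Testing and Study Schedule lists the same data for both cohorts at 1, 3, 6 and 12 months. These include tacrolimus level, BK, CMV, donor specific antibody, and surveillance biopsies at 3 and 12 months. Statistical analysis names the chi-square test, a t-test and Kaplan-Meier curves. It mentions no adjustment or stratification.

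**The concern.** Every Envarsus patient has exposure directed by the protocol, and every control has whatever management was given at the time. If the two differed, a difference in toxicity could reflect formulation, target level, the response to test results, or a mixture of these.

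Two features make this more than a general complaint about historical controls. First, the results that trigger a change in level are themselves the endpoints. A 3-month biopsy finding can alter exposure before the 12-month biopsy is read; this feedback is written into one arm and left undescribed in the other. Second, the Introduction itself treats exposure as important: it describes a narrow therapeutic window that calls for monitoring and individual titration.

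What is at stake is whether the result can be read as an effect of formulation. Different management could mimic a benefit of Envarsus or hide one.

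**Working it through.** **Comparing what is specified for each cohort**

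| Feature | Prospective Envarsus arm | Retrospective controls |
|---|---|---|
| Target level | 8-10 ng/mL | Not stated |
| Level changed on biopsy, BK, CMV or antibody results | Yes | Not stated |
| Surveillance biopsies at 3 and 12 months | Yes | Listed in the data schedule |
| Level, BK, CMV, antibody at 1, 3, 6, 12 months | Yes | Listed in the data schedule |
| Analysis that uses attained level | None | None |

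The sentence on modifying the level names no arm. It stands in the Envarsus section and is in the future tense, so it cannot govern care already given to controls. The cohorts are therefore described alike for monitoring, but only one is described for the target and for how results were acted on.

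**Does the 3-month biopsy avoid the problem?** Only in part. It comes before any change driven by a surveillance biopsy. A difference in target would act from transplant, and BK, CMV and antibody results are collected at 1 month and can also change the level.

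**Illustration of scale.** The plan has no power calculation, alpha or event rate to reproduce. Assumptions not in the documents: 100 controls (1:1 matching), two-sided alpha 0.05, the toxicity rates shown, and no formulation effect, so that management alone produces the difference.

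Normal approximation, with n = 100 per group and p̄ the mean of the two rates:

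P(significant) ≈ Φ[(|p1 − p2| − 1.96·SE0) / SE1], where SE0 = √(2p̄(1 − p̄)/n) and SE1 = √((p1(1 − p1) + p2(1 − p2))/n).

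For 30% versus 20%:

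- SE0 = √(2 × 0.25 × 0.75/100) = 0.0612
- SE1 = √((0.21 + 0.16)/100) = 0.0608
- (0.10 − 0.1200)/0.0608 = −0.329, and Φ(−0.329) = 0.371

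Exact binomial enumeration of the chi-square test gives:

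| Assumed rates | Uncorrected | With continuity correction |
|---|---|---|
| 30% vs 25% | 12.4% | 9.4% |
| 30% vs 20% | 37.1% | 31.3% |
| 40% vs 30% | 31.6% | 26.3% |

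With equal rates of 30%, the uncorrected test rejects 5.1% of the time, so the excess comes from the assumed difference. By the approximation, with control rates from 20% to 50%, a 5-point shift gives 15.1% down to 10.5%, and a 10-point shift 50.8% down to 29.4%. With 200 controls the 10-point range is 60.1% down to 37.2%.

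**The case against.** The strongest reply is that a protocol cannot prescribe care already given, so its silence about controls does not show that their care differed. The schedule points towards similar monitoring, with the same visits, tests and surveillance biopsies. Level-guided titration is also described as necessary for tacrolimus in general, so it is not peculiar to Envarsus. All of this stands, and it is why the concern is possible confounding rather than demonstrated confounding.

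Four stronger readings are tempting, and the documents do not support them:

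- *Controls were managed differently, and any benefit could be put down to that.* No section describes control management, so neither a difference nor its direction is shown.
- *The plan commits itself to crediting the whole difference to formulation.* It never says so. The hypothesis compares patients who receive each drug, which can be read as treatments as managed, and the study is called observational.
- *The percentages are this trial's false-positive rate.* They are the power of a test at differences assumed for illustration, under an assumed 1:1 ratio and an alpha that the plan does not state.
- *The 3-month biopsy, or a subset with similar month-1 levels, isolates formulation.* The 3-month result remains open to a target difference and to month-1 results. A month-1 level is measured after treatment starts. The Introduction reports about 30% greater bioavailability, so level may be part of how formulation acts, and selecting on it can introduce bias of its own.

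It may also be said that this is one instance of a wider gap, a historical control with unspecified matching. That is fair, but the use of endpoint results to alter exposure is specific to this point and needs its own wording.

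**Conclusion.** The concern holds as a limit on interpretation. The target and the result-driven changes are specified only for the Envarsus arm, two of the triggers are endpoints, and controls are defined by formulation alone. The planned unadjusted analyses cannot separate formulation from exposure management.

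The direction and size of any bias are unknown. The illustrative rejection rates show only that a moderate management difference, if one existed, could often produce a significant result at about this sample size. If chart review shows that controls were managed comparably, the concern largely falls away. If it does not, the 12-month result supports a statement about strategies and not about formulation. The point should be acted on before controls are selected.

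**What to change.** 1. In Patient Recruitment, add that the target range and level-adjustment practice applied to each control will be recorded by chart review. Restrict to, or match on, controls managed to a comparable target with the same surveillance-biopsy and antibody-monitoring practice.
2. In Statistical analysis, require attained tacrolimus level at 1, 3, 6 and 12 months to be reported for both cohorts beside the primary result. These data are already collected.
3. Report the 3-month and 12-month biopsy results separately. State that the 3-month result precedes only surveillance-biopsy-driven changes and does not by itself isolate formulation.
4. Describe the 12-month result as a comparison of treatment strategies unless control management is shown to be comparable.
5. Do not restrict the comparison to patients with similar month-1 levels. If such an analysis is wanted, label it exploratory, because it conditions on a post-treatment variable.
6. If rejection percentages are cited, present them only as an illustration under assumed rates, 1:1 matching and alpha 0.05.

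The cost is protocol wording, chart review, a smaller pool of eligible controls and possibly a narrower claim. No clinical target or rule needs to change.
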